#### **Slope criterion:**

The regression slope assessment in each preceding 5-day rolling period:

- (d) Morning PEF slopes  $\leq -3\%/day$ .
- (e) Daily total rescue medication slope  $\geq 0.4$  doses/day
- (f) Slope  $\geq 0.2$ /day in all of symptom scores breathlessness, cough, sputum.

The slope criterion is met if [(d), (e) and (f)] are all met, and at least one of [(a), (b) or (c)] is met.

In all of the above cases, the regression slope is the point estimate of the slope obtained from a linear regression of the absolute values of each of the variables separately against day number, with no other variables included in the regression model.

A regression slope will be calculated provided there are at least 2 non-missing values in the required 5 days. If one or more of the variables above (d, e or f) does not have at least 2 non-missing values in the required 5 days, then the slope requirement cannot be met.

For morning PEF, the regression slope thus obtained will first also be divided by the baseline PEF value before applying the above criterion.

The following table shows how the timing for the 5-day requirement for the regression slopes fits with the 2-consecutive day requirement, where "Day 0" here refers to the first of the 2 consecutive days (shaded) to be used each time the rolling 2 consecutive day assessment is made:

	Day -4	Day -3	Day -2	Day -1	Day 0	Day 1
Threshold (a), (b), (c)					x	x
Slope	х	х	х	х	х	

 Table 21
 Timing for assessment of COPDCompEx slope criterion

A diary event can occur when (i) the threshold deterioration criterion is met for at least 2 diary variables, or when (ii) the threshold deterioration criterion is met for one diary variable, and the slope criterion is fulfilled for all included variables. In case of (i), the diary event is defined to start on the first day of the 2 consecutive deterioration days (event days 0–1). Any missing data in this 2-day window will make the event missing. In case of (ii), the event is defined to start on the first of the 2 days fulfilling the threshold criterion. This means that the slopes are calculated for days -4 to 0 of an event. At least 2 days with data are needed to calculate slopes, otherwise the event is considered missing.

#### Start and End dates of COPDCompEx events

The start date of a CompEx event is defined as the earliest of the exacerbation or objective deterioration start dates which meets the definition. Objective deterioration start date is defined as the earliest Day 0 (in notation from Table 21) from any series of rolling 2 consecutive days which first qualifies using either the threshold or slope criterion.

The end date of a CompEx event is defined as the latest of the exacerbation or objective deterioration end dates which meets the definition. Objective deterioration end date is defined as the latest Day 1 (in notation from Table 21) from any series of rolling 2 consecutive days which last qualifies using either the threshold or slope criterion.

If the end date of the first CompEx event and the start date of the second CompEx event are less than 7 days apart for any participant, then these will be counted as one CompEx event.

For CompEx analyses, only on-treatment events (events occurring from randomization first dose of study intervention up to and including 28 days post last dose) will be considered.

### **3.3.4.1** Time to first COPDCompEx event

Time to first COPDCompEx event is the secondary endpoint of the study.

Time to first COPDCompEx event (days) will be calculated as: [Start date of first event or censoring – date of the first dose of study intervention+ 1].

Date of first event will be the first start date of a COPDCompEx event as defined above. For participants who do not experience an on-treatment COPDCompEx event, date of censoring will be the minimum of date of last dose plus 28 days, or last day of eDiary recording if sooner.

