## 8.1.8 Patient Reported Outcome Questionnaires

Electronic PRO questionnaires will be completed every day at home and at site visits (as specified in the SoA [Section 1.3]) using a hand-held device. Site personnel and participants will be provided training on the use of the device. For home use, the device will be programmed to automatically alert the participants when to fill out the ePROs. In addition, participants will bring their device to study visits, to use for collection of clinic ePROs, which should be completed as the first clinic assessment. The clinic ePROs will be filled out in this order: ER-S:COPD, cough VAS, BCSS, CCI SGRQ, CAT, CCI and Study Participant Feedback Questionnaire. Detailed procedures for using the device will be described in a separate instruction manual provided to each site.

AstraZeneca

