Data presentations	11May2023	Section 3.1.5 Added clarification for screening and re-screening visits. CCI Added visit windowing for coagulation, CCI CCI and cough monitoring. PK will have no analysis visit windows, the CRF visit will be used instead. Updated labelling of weekly periods for CCI and eDiary variables. Section 3.1.6 Updated of vital signs timepoint labelling. Sections 3.1.7, 3.8.1 Study phase windows have been updated.	Updated to avoid issues that could occur during analyses.
Statistical analysis method for the primary or secondary endpoints	11May2023	Subgroup analysis: Sections 3.1.9, 4.2.5.1, 4.2.5.3, 4.2.8.2: Subgroup analysis of extent of emphysema for secondary CCI endpoints has been added.	Updates according to CSP Amendment 4, Amendment 5 and as per requests from the team.

		Sections 3.1.9 and 3.2.1 updated geographical region subgroup: North America has been merged with Western Europe CCI CCI Section 3.1.9 and 3.2.1: Age subgroup updated. CCI Added clarification regarding modalities of subgroups.	
Other: new countries	11May2023	Section 3.2.1: Australia, New Zealand, Czech Republic added.	Updates due to addition of new countries to the study.
Other: smoking status	11May2023	Sections 3.2.5, 4.2.3.5: added definition and details for the overall smoking status. Sections 3.1.9, 4.2.5.1, 4.2.8.3, 4.2.8.4, 4.2.8.5: added new analysis by smoking status subgroup.	Added as per request from the team.
CCI	CCI	CCI	CCI
Other: COPDCompEx	11May2023	Section 3.3.4 Lack of efficacy rules removed. Replace evening/morning pairing instead of morning/evening. On-treatment events definition added. Section 3.3.4.1 Updated date of censoring. Section 4.2.5.1 CompEx criteria by patient will be also listed.	Removed "Lack of efficacy" since it is not one of the reason possible in case of treatment discontinuation. Updated pairing to be consistent with other endpoints in the study. Date of censoring was updated to avoid any issues with patients which stopped providing eDiary information before end of treatment.

Other: SGRQ	11May2023	Sections 3.4.4, 4.2.5.5 analyses by domain score for SGRQ will be also provided.	To get detailled results from each domain score and not only for the total score.
Other: immunogenicity variables	11May2023	Sections 3.6.1 and 3.6.2: Removed nAb response.	Removed as we will not need the nAb for this study.

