## **3.3.4 COPDCompEx events**

The COPDCompEx is a composite endpoint for exacerbations in COPD. The COPDCompEx combines exacerbations with events defined from participant e-Diaries and PEF.

Note the COPDCompEx definition typically includes dropout due to lack of efficacy as a CompEx event. However, since 'lack of efficacy' is not listed as a reason for drop out in this study, we will not include the drop out criterion for COPD CompEx in this study.

A participant will be considered to have a CompEx event during the planned Intervention Period if the participant has one or more of the following:

- COPDCompEx defined exacerbation, those collected in eCRF with at least one of the following criteria met:
  - Associated Hospitalizations = Yes;
  - Systemic Corticosteroids (injected and/or oral) = Yes;
  - Antibiotics = Yes;
  - Any emergency room visit due to COPD exacerbation? = Yes.
- A diary event An objective deterioration, which is defined as either the threshold criterion or the slope criterion (or both), being met for ≥2 consecutive days. See derivation below.

For this purpose, "2 consecutive days" means strictly the same 2 consecutive days when assessing multiple requirements within those days. For the eDiary data (which is captured twice during the day), one day will be defined by the evening/morning pairing as the other eDiary endpoints in this trial. Diary data recorded in the evening of day n and in the morning of day n+1 will belong to study day n.

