## 3.4.4 St George's Respiratory Questionnaire

The SGRQ is a 50-item PRO instrument developed to measure the health status of patients with airway obstruction diseases (Jones et al 1991). The SGRQ yields a total score and three domain scores (symptoms, activity, and impacts). The total score indicates the impact of disease on overall health status. This total score is expressed as a percentage of overall impairment, in which 100 represents the worst possible health status and 0 indicates the best possible health status. Likewise, the domain scores range from 0 to 100, with higher scores indicative of greater impairment. Specific details on the scoring algorithms are provided by the developer in a user manual (Jones and Forde 2009). The principle of calculation of total score and domain scores in accordance with the abovementioned user manual are provided in Appendix B 3.

The SGRQ will be completed using the eDiary in accordance with the SoA (CSP Section 1.3), and a 4-week recall version will be used.

The key outcome variable for the SGRQ will be the change in total SGRQ score from baseline to Week 12, but the change in total score from baseline to Week 4 and Week 28 will also be derived (see Section 3.1.3). Change in the domain score from baseline to Week 4, Week 12 and Week 28 will also be derived.

Other variables based on SGRQ to report include:

- Proportion of participants with a decrease in SGRQ score of ≥ 4 points from baseline to Week 12 (Yes=1/No=0)
  - Yes: change from baseline SGRQ score to SGRQ score at Week  $12: \le -4$
  - No: change from baseline SGRQ score to SGRQ score at Week 12: > -4
- Proportion of participants with a decrease in SGRQ score of ≥ 4 points from baseline to Week 28 (Yes=1/No=0)
  - Yes: change from baseline SGRQ score to SGRQ score at Week  $28: \le -4$
  - No: change from baseline SGRQ score to SGRQ score at Week 28: > -4

Participants with missing or non-evaluable SGRQ score will be considered as not achieving SGRQ response.

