#### Hypothesis testing of secondary endpoints

To account for multiplicity to test the primary endpoint (change from baseline in pre-BD  $FEV_1$  at Week 12) and key secondary endpoints, the Hochberg procedure will be used to control the overall type I error rate.

Let  $H_0$  denote a null hypothesis as stated above, and  $H_1$ ,  $H_2$ ,  $H_3$ ,  $H_4$  denote null hypotheses tested on key secondary endpoints:

H1: Difference in time to first COPDCompEx event at Week 28 (MEDI3506-placebo) = 0.

H2: Change from Baseline in daily cough frequency at Week 12 (MEDI3506-placebo) = 0.

H3: Change from Baseline in R5-R20 at Week 12 (MEDI3506-placebo) = 0.

H4: Change from Baseline in mean BCSS score (over the previous 4 weeks) at Week 12 (MEDI3506-placebo) = 0.

Let  $p_i$  denote the p-value for the hypothesis  $H_i$ , where i = 1...4. Let  $p_{(1)}$ ,  $p_{(2)}$ ,  $p_{(3)}$ ,  $p_{(4)}$  denote ordered p-values starting from the largest, and the ordered hypotheses  $H_{(1)}$ ,  $H_{(2)}$ ,  $H_{(3)}$ ,  $H_{(4)}$  corresponding to them.

The testing strategy will be as following:

The procedure begins with testing of the  $H_0$  null hypothesis is tested at the full alpha level of 0.1. If the one-sided p-value is less than 0.1, then null hypothesis will be rejected, and the procedure go to Step 1.

- Step 1. The largest p-value  $p_{(1)}$  is compared to its alpha critical value,  $\alpha_1 = 0.1$ . If  $p_{(1)} > \alpha_1$ , then accept and declare non-significant the hypothesis H(1) and go to the Step 2. Otherwise testing stops and all remaining hypotheses are rejected and declared significant.
- Step 2. Calculate new  $\alpha_2 = 0.1/2$ . If  $p_{(2)} > \alpha_2$ , then accept and declare non-significant the hypothesis H(2) and go to the Step 3. Otherwise testing stops and all remaining hypotheses (which have smaller p-values) are rejected and declared significant.
- Step 3. Calculate new  $\alpha_3 = 0.1/3$ . If  $p_{(3)} > \alpha_3$ , then accept and declare non-significant the hypothesis H(3) and go to the Step 4. Otherwise testing stops and all remaining hypotheses (which have smaller p-values) are rejected and declared significant.
- Step 4. Reject  $H_{(4)}$  if  $p_{(4)} \le 0.1/4$ .

The Hochberg procedure is available in PROC MULTTEST (specifying the HOCHBERG option).

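### Time to first COPDCompEx keeps follow-up after the diary stops only when it contains an event, which overstates Kaplan-Meier risk and biases the H1 hazard ratio if diary stopping differs by arm

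*SAP*

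**What the plan says.** - **What counts as an event.** Under SAP Section 3.3.4 either component is enough. One is a "COPDCompEx defined exacerbation, those collected in eCRF with at least one of the following criteria met": hospitalisation, systemic corticosteroids, antibiotics or an emergency room visit. The other is a diary event derived from home data. Only the second needs the diary.
- **Event window.** SAP Section 3.3.4, on start and end dates, says that "only on-treatment events (events occurring from randomization first dose of study intervention up to and including 28 days post last dose) will be considered". It sets no limit at diary stop.
- **Censoring.** SAP Section 3.3.4.1 applies a shorter limit, and only to participants without an on-treatment event: "date of censoring will be the minimum of date of last dose plus 28 days, or last day of eDiary recording if sooner".
- **Reason given.** The SAP amendment history explains: "Date of censoring was updated to avoid any issues with patients which stopped providing eDiary information before end of treatment".
- **Role.** The endpoint is tested as H1, "Difference in time to first COPDCompEx event at Week 28 (MEDI3506-placebo) = 0", in the Hochberg family that opens only if FEV1 succeeds (SAP Section 4.1.1). The analysis is a Cox model with a Kaplan-Meier plot (SAP Section 4.1.6).
- **Table text.** The note to Table 14.2.2.2.4 in SAP Appendix A says that the Cox analysis uses available data over the whole period to Week 28 for everyone. That does not fit diary censoring.

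**The concern.** Whether a day of follow-up counts should not depend on whether an event later occurs. Here it does. Take two participants who both stop the diary on day 60 and keep dosing. One has an eCRF exacerbation on day 150 and contributes 150 days and an event. The other has none and contributes 60 days. Between days 61 and 150 the second was observed and event-free, but is missing from the risk set.

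The situation is foreseeable. Exacerbations are assessed at scheduled visits or at an extra visit, whatever the diary use (Protocol Section 8.1.6). Participants who stop study drug still attend their remaining visits (Protocol Section 7.1). The amendment history shows that early diary stop was expected. The change dealt with non-events and put no matching limit on events.

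At stake are the Kaplan-Meier curves and the hazard ratio for a key secondary endpoint. Protocol Section 4.1 relies on that endpoint to show wider efficacy beyond FEV1.

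**Working it through.** **The plan's own figure.** The only sample size stated is for FEV1: n per arm = 2(z₀.₉₀ + z₀.₈₀)² × (SD/difference)² = 2 × (1.2816 + 0.8416)² × (250/90)² = 69.6, so 70 per arm. Power at 70 is 0.802. For dropout, 140/0.98 = 142.9, rounded up to 144 (72 per arm). This reproduces, but it does not bear on COPDCompEx. The documents give no event rate, hazard ratio, power or diary-stopping rate for that endpoint, so every rate below is an assumption.

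**Mechanism in one calculation.** Assume a 28-week (196-day) eCRF risk of 35%, so the daily hazard is −ln(0.65)/196 = 0.00220. Take 100 event-free participants who stop the diary on day 98 and keep dosing.

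- Expected eCRF events in the remaining 98 days: 100 × (1 − √0.65) = 19.4. All are counted.
- True person-days in that period: 19.4/0.00220 ≈ 8,816.
- Person-days dropped, from those who stay event-free: 80.6 × 98 ≈ 7,901.
- Person-days kept: about 915. The apparent hazard is 8,816/915 ≈ 9.6 times the true one.

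Across an arm this is diluted by participants who never stop the diary.

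**Simulation set-up.** 72 per arm over 196 days, with exponential event times. The eCRF/diary risks are 25%/35%, 35%/25%, 35%/35% or 45%/20%. Stop times are uniform and unrelated to risk. Diary events are visible only until stop, stoppers keep dosing, and no later eDiary entry counts. Hazard ratios come from 400,000 per arm. Error comes from at least 2,500 trials per setting, with Monte Carlo error of about 0.6 points (√(0.1 × 0.9/2,500)).

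*Equal stopping, true HR 1.0.* The true Week 28 risk is 51 to 58% (for example 1 − 0.65 × 0.65 = 57.75%).

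| Stopping in each arm | Kaplan-Meier risk overstated by | Events (of 144) leaving under a common cut-off |
|---|---|---|
| 10% | 0.7 to 1.2 points | 1.5 to 2.7 |
| 20% | 1.5 to 2.4 points | 2.9 to 5.4 |
| 30% | 2.5 to 3.8 points | 4.5 to 7.9 |

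The hazard ratio stays at 1.00. A common cut-off returns the true Kaplan-Meier risk to within 0.2 points.

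*Unequal stopping, true HR 1.0, current rule.*

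| Stopping, active/placebo | HR | One-sided error (nominal 10%) |
|---|---|---|
| 10%/15% | 0.98 to 1.00 | 10 to 12% |
| 15%/10% | 1.01 | 9 to 10% |
| 10%/20% | 0.97 to 0.99 | 10 to 12% |
| 20%/10% | 1.02 to 1.03 | 8 to 9% |
| 10%/30% | 0.94 to 0.96 | 13 to 16% |
| 30%/10% | 1.04 to 1.06 | 6 to 8% |

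The arm with more stopping looks worse. A common cut-off at home-diary stop gives HR 0.99 to 1.01 and error 9 to 11% throughout.

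*True HR 0.70, 20-point gap (risks 35%/35% and 45%/20%).* With more stopping on placebo, the current rule gives HR 0.66 to 0.67 and power 66 to 68%. With more stopping on active, it gives HR 0.73 to 0.74 and power 48 to 51%. The common cut-off gives HR 0.70 and power 54 to 58%.

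*Stoppers who also stop dosing.* Their event window closes within 28 days of the last dose. If all stoppers do so, the HR is 0.99 to 1.02 and error 9 to 11%, even with a 20-point gap.

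**The case against.** **The effect is small at plausible gaps.** With about 80 events, SE(log HR) is about 2/√80 = 0.22. Even a 20-point gap shifts log HR by only about a quarter of that. Run-in compliance of at least 70% (Protocol inclusion criterion 11), adherence checks at each visit and blinding all work against large or unequal stopping. This stands, and limits the point for the hazard ratio. It does not remove the Kaplan-Meier bias, which needs no difference between arms.

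**The last eDiary day might be read as including clinic entries, which would reverse the bias.** Protocol Section 8.1.8 says "participants will bring their device to study visits, to use for collection of clinic ePROs, which should be completed as the first clinic assessment", and the SAP says "The SGRQ will be completed using the eDiary in accordance with the SoA". If every stopper had a counted Week 28 clinic entry, a 20-point gap would give HR 1.03 to 1.05 where the plain reading gives 0.94 to 0.96. A reader might infer that the direction is therefore unknown. The documents do not favour that reading. SAP Section 3.3.4 describes eDiary data as twice-daily entries paired evening to morning, and the Schedule of Activities lists SGRQ separately from daily home use. One clarifying line is enough.

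**Diary events do not always need gap-free data.** The sentence "Any missing data in this 2-day window will make the event missing" is stated for the threshold route. A single non-missing rescue-use entry can stand in for the day, and slopes need only two of five days. This is correct, so the cut-off should be defined by whether a diary event can be assessed.

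**A common cut-off discards real exacerbations inside the stated period to Week 28.** This stands as a trade-off. It is the reason to keep the current rule as a sensitivity analysis.

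**Other analyses exist.** A negative binomial rate analysis is visible (SAP Section 4.1.5), but its at-risk time is not defined in the visible text. Section 3.3.4.2 and several exacerbation tables are redacted. It would be wrong to infer that no supportive analysis is planned.

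**Conclusion.** The mismatch is in the SAP text and needs no assumed rate: events run to last dose plus 28 days, while event-free time stops at the last eDiary day if sooner. No visible passage repairs it.

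Its size does rest on assumptions, namely 28-week risks of 25 to 45% (eCRF) and 20 to 35% (diary), 10 to 30% stopping, and stopping unrelated to risk among participants who keep dosing. On these, Kaplan-Meier risk is overstated by about 1 to 4 points even with equal stopping. The H1 hazard ratio moves by about 1 to 3% for a 5- to 10-point gap between arms and about 4 to 6% for a 20-point gap. In the 20-point case one-sided error is about 6 to 8% or 13 to 16%, depending on which arm stops more.

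A reader might infer that the H1 result will be biased, or biased towards the drug. The documents support neither: they give no stopping rates and no reason to expect a difference by arm. The primary FEV1 analysis is unaffected, and H1 is tested only if FEV1 succeeds. The rule is worth correcting because the correction is cheap, not because the trial's main conclusion is at risk.

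**What to change.** 1. Set one end-of-ascertainment date per participant: the earlier of last dose plus 28 days and the last home-diary day on which a CompEx diary event can be assessed. Apply it to events and non-events alike in the Cox and Kaplan-Meier analyses. State that clinic-only questionnaire entries such as SGRQ do not count as eDiary recording. Reconcile the note to Table 14.2.2.2.4.
2. Report the current rule, with eCRF exacerbations counted to last dose plus 28 days, as a sensitivity analysis, because diary stopping may follow worsening disease. Tabulate diary stopping, and eCRF exacerbations after it, by arm.

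**Cost.** SAP wording, one extra analysis and one table, with no new data. About 1 to 6 of roughly 65 to 80 events leave the main analysis. The most extreme setting checked (30% stopping in both arms, eCRF risk 45%) loses about 8. If exacerbations themselves end diary entry the loss is larger: with 20% stopping in each arm and 15 to 30% of eCRF events ending entry, 9 to 22 events leave, and power at a true HR of 0.70 is 50 to 56% against 57 to 60% under the current rule. A common cut-off does not by itself remove informative censoring, so the sensitivity analysis and the table should be read beside it.

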# **3.4** Patient reported outcome variables

## **3.4.1** Evaluating Respiratory Symptoms in COPD (E-RSTM: COPD)

Change from baseline to Week 12 in 4-weekly mean ER-S: COPD is a secondary endpoint of this study.

The E-RSTM: COPD is an 11-item PRO developed to evaluate the severity of respiratory symptoms of COPD. Summation of E-RSTM: COPD item responses produces a total score ranging from 0 to 40, with higher scores indicating greater severity. In addition to the total score, symptom domain scores can be calculated for breathlessness (5 items; score range: 0 to 17), cough and sputum (3 items; score range: 0 to 11) and chest symptoms (3 items; score range: 0 to 12) by summing the responses of items within a respective domain. As with the total score, higher domain scores indicate greater severity (see Appendix B 1).

